5.1.2.4 Ongoing Studies in Other Indications

A Phase 1b/2a study (KD019-204) of the combination of trastuzumab and tesevatinib is ongoing in subjects with HER2+ metastatic breast cancer (study KD019-204). The Phase 1 portion of the study used a 3+3 design that is commonly used in oncology studies. The Phase 1 portion of the study has determined that 300 mg daily of tesevatinib in combination with trastuzumab is the MTD dose, as the two subjects treated with 350 mg daily had Grade 3 events considered to be at least possibly related to tesevatinib (one had Grade 3 diarrhea not recovering to Grade 1 by seven days, and the other had Grade 3 QTc prolongation confirmed by central reading).

A Phase 1b/2a study (KD019-101) of tesevatinib in patients with ADPKD is ongoing. Subjects with ADPKD, in whom the drug will be administered chronically for years, did not tolerate the Grade 2 acneiform skin rash, which occurred in 2/5 patients at 150 mg daily. In addition, there were 2/8 patients receiving tesevatinib at a dose of 100 mg daily who had asymptomatic prolongation of the QTc duration (one Grade 3 and one Grade 2). Daily doses below 50 mg are being evaluated further.

5.2 Safety Profile of Tesevatinib

5.2.1 Tesevatinib

AEs that have been associated with tesevatinib include the following: diarrhea, skin rash, QTc(F) prolongation, elevated serum creatinine, elevated serum amylase, and interstitial lung disease (see Warnings, Precautions, and Management in Section 11.1.3).

Diarrhea: Diarrhea is an expected AE for agents like tesevatinib that have significant EGFR inhibitor activity. Grade 3 diarrhea was the dose-limiting toxicity (DLT) for both the 5 days out of 14 days schedule of tesevatinib in study XL647-001 as well as for the daily dosing of tesevatinib in the KD019-204 study of tesevatinib in patients with metastatic breast cancer. At

doses below those that cause DLT, diarrhea has generally been manageable with anti-diarrheal medications such as loperamide.

Skin Rash: Acneiform skin rash is an expected AE for agents like tesevatinib that have significant EGFR inhibitor activity. The rash characteristically involves the chest and face. Paronychia involvement, although characteristic of EGFR inhibitors, has not been seen in tesevatinib studies.

QTc(F) Prolongation: In clinical trials of tesevatinib, cases of QTc(F) prolongation have been observed.

Common Terminology Criteria for Adverse Events (CTCAE v4.03) was used to assign the severity grade for QTc(F) AEs and the criteria for each grade are presented below.

	Grade 1	Grade 2	Grade 3	Grade 4
ProlongedQTc(F) interval	> 450–470 msec	> 470–500 msec or ≥ 60 msec above Cycle 1 Day 1	> 500 msec	> 500 msec with life threatening signs or symptoms; torsades de pointes

In the 169 subjects with malignancies treated in 4 uncontrolled studies, the majority of whom had advanced, metastatic non-small cell lung cancer, 33 (20%) were found to have QT prolongation based on machine read ECGs at some time during treatment that met the CTCAE v4.03 definition of an AE: Grade 1 [7 (4%) subjects], Grade 2 [14 (8%) subjects], and Grade 3 [12 (7%) subjects]. The majority of these subjects received ≥ 300 mg daily or 350 mg given for 5 days with 9 days off. There were no clinical findings associated with the ECG changes. There were no reports of QTc(F) prolongation in 32 healthy volunteer subjects who received a single 300 mg dose of tesevatinib.

Clinical trial data available for review encompassed Studies XL647-001, XL647-002, XL647-201, XL647-203, and XL647-004. Other studies (XL647-005) did not have data confirmed by central ECG laboratory. In terms of total exposure, 201 subjects received tesevatinib (169 subjects with cancer and 32 normal volunteers). ECGs for a total of 178 of these subjects have been reviewed by the central ECG laboratory.

No SAEs of convulsion; sudden death; ventricular tachycardia, fibrillation, or flutter, or torsades de pointes have been received for the > 250 subjects exposed to tesevatinib.

Digital ECG files from 178 subjects were supplied to a vendor (eRT) for analysis. ECGs from 60 subjects had further review by a cardiologist, including all 41 subjects in XL647-203, and an additional 19 subjects from XL647-001 (2), XL647-002 (12), and XL647-201 (5), because they were reported to have noteworthy QTc(F) prolongation on the ECG machine analysis.

Of these 60 subjects, eRT analyzed the digital files and identified 23 (38%) subjects who had no outlier findings, 5 (8%) subjects who had no QTc(F) prolongation on the digital analysis, and 2 (3%) subjects who eRT could not completely exclude as being product related, but whose prolonged QTc(F) value obtained on the machine read ECG was not felt to be measurable due to underlying RBBB or atrial fibrillation.

Of the 30 (50%) remaining subjects, eRT identified 25 with prolonged QTc(F) values of ≤ 60 msec, which eRT could not completely exclude as being product related. There were 3 subjects with QTc(F) > 60 msec that were felt to be possibly/probably related to drug treatment and 2 subjects who had QTc(F) values > 500 msec, which were felt to be probably related to drug treatment.

A preliminary analysis of delta QTc(F) (change from Cycle 1 Day 1 value) versus plasma concentration was carried out using pooled data from studies with intermittent 5 days on and 9 days off dosing (Study XL647-001), single doses with crossover food effects (Study XL647-004) and once-daily dosing (Studies XL647-002 and XL647-203) regimens. Concentration-matched ECGs were available from 1104 records from 125 subjects. This analysis was done using QTc(F) values obtained from the central ECG laboratory. All ECGs digitized and read at a central laboratory and QTc(F) values were Fridericia corrected. The QTc(F) versus concentration relationship was described using linear, power, and E_{\max} mixed effects models using bootstrap population parameter estimates pooled across all three models (i.e., ~ 1000 bootstrap estimates per model). Analyses showed that the concentration-QTc(F) relationship appears to be consistent across Studies XL647-001, XL647-002, XL647-004, and XL647-203 (i.e., suitable for pooling, and argues against a marked time effect because XL647-004 is single dose). In these studies, QTc(F) prolongation increased with increasing plasma concentration.

In study KD019-101, subjects treated with doses of tesevatinib as low as 100 mg daily have had prolongation of QTc(F) of > 60 ms over Cycle 1 Day 1 levels. In study KD019-204, one of two subjects receiving tesevatinib at 350 mg daily in combination with trastuzumab had QTc(F) prolongation to > 500 ms, which was a DLT event for that study. Subjects in this study will be monitored carefully for QTc prolongation, and a central laboratory will review all ECGs in this study.

Elevations of Serum Creatinine: Data from study KD019-101 indicate that subjects with ADPKD receiving tesevatinib have experienced elevations of creatinine without elevations in cystatin C. For instance, the median changes from screening values for creatinine and cystatin C from all 9 subjects in the 50-mg dose cohort reveal that creatinine values were increased by 7.5% at Day 3, by 22% at Day 7, and increased by 13% at Day 28. Data after Day 28, including two subjects who have received tesevatinib for 16 months, do not indicate any significant ongoing change in creatinine. Cystatin C levels, during the same time periods, did not change, indicating that the increases in serum creatinine may not be reflective of changes in kidney function. Data from the subjects other doses of tesevatinib exhibited a similar pattern. This increase in creatinine occurs early and after approximately 7 days, does not continue to increase, similar to the increase in serum creatinine seen with cimetidine. Increases in creatinine were seen in previous clinical trials of tesevatinib. For example, increases in serum creatinine in 10% of subjects were reported in Study XL647-201. However, most of the previous studies were in subjects with malignancies, and in previous studies, cystatin C levels were not evaluated, so increases in serum creatinine that may not represent renal dysfunction were not recognized.

In order to further investigate the effects of tesevatinib on serum creatinine levels, the effects of tesevatinib on a panel of transporter molecules (including OCT2 and MATE) were evaluated in vitro. The results indicate that tesevatinib potently inhibits MATE1 and MATE2-K transporter proteins. MATE transporter proteins carry creatinine out of kidney proximal tubule cells into the tubule lumen. Inhibition of MATE transporter proteins decreases secretion of creatinine into the proximal tubule lumen and leads to an increase in serum creatinine levels. Increases in creatinine appear to be reversible. Both serum creatinine and cystatin C will be evaluated in this study in order to provide more information about any changes in creatinine that occur.

Elevations of Serum Amylase: There have been occasional cases of asymptomatic elevation of serum amylase in subjects treated with tesevatinib. In KD019-101, a study treating subjects with polycystic kidney disease at doses up to 150 mg/day, 5 subjects had amylase levels above the normal limit, 2 of which had elevated levels at screening. None had symptoms of clinical pancreatitis.

Previous oncology studies of tesevatinib have been reviewed for cases of elevated amylase or pancreatitis. Amylase was not routinely evaluated in any of these previous studies. There was only 1 treatment-emergent adverse event (TEAE) of an increased amylase level or of possible pancreatitis. This was an elevation of amylase to 922 U/L without clinical pancreatitis in a subject with Stage IV non-small cell lung cancer who received tesevatinib at a dose of 300 mg/day. On serum amylase isoenzyme analysis, the subject had an elevation in salivary

amylase. The investigator's conclusion was that the subject appeared to have an increase in amylase due to salivary amylase secretion by the tumor. To date, no subjects receiving tesevatinib have had symptoms compatible with clinical pancreatitis.

Interstitial Lung Disease: Non-fatal interstitial lung disease (ILD) has been reported in association with the use of tesevatinib in one subject with NSCLC out of >250 subjects exposed to tesevatinib.

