	
RECIST 1.1 response, and an over 90% chance of at least 2 subjects having a response. All subjects who take at least one dose of study drug will be evaluable for safety and efficacy assessments.
 
Treatment-emergent AEs will be summarized using the Medical Dictionary for Regulatory Activities (MedDRA[®]) (Version 18.1 or higher) System Organ Class (SOC) and preferred term, classified from verbatim terms. The incidence and percentage of subjects with at least one occurrence of a preferred term will be included, according to the most severe grade using the National Cancer Institute Common Terminology Criteria for Adverse Events (NCI-CTCAE; Version 4.03). The number of events per preferred term will also be summarized. Causality (relationship to study treatment) will be summarized separately.
 
AEs, SAEs, related AEs, related SAEs, \geq Grade 3 AEs, related \geq Grade 3 AEs, and AEs leading to withdrawal, dose modification, or treatment discontinuation will be summarized by cohort and tesevatinib overall according to SOC and preferred terms. AEs will also be summarized in listings. Duration of AEs will be determined and included in listings, along with action taken and outcome.
 
Descriptive statistics including 95% confidence intervals for improvement in symptoms attributed to leptomeningeal metastases, clearing of NSCLC cells in the CSF, and clearing of CNS MRI findings will be presented. Exploratory evaluation of efficacy results by EGFR mutation will be performed.
 
In addition, identical statistics for the change and percent change from Cycle 1 Day 1 tumor measurements will be presented. These analyses will be done after each two cycles of therapy, and will include peripheral (non-CNS) tumors as well as brain metastases. Summary statistics will be produced for PFS and OS. The percentage of subjects without disease progression after 3 and 6 months of dosing will also be presented separately by local and central radiograph results.
 
Laboratory results will be classified according to NCI-CTCAE Version 4.03 and summarized by cohort. Laboratory results not corresponding to a coded term will not be graded. Incidence of laboratory abnormalities will be summarized. The worst on-study grade after the first dose of study drug will be summarized. The incidence of \geq Grade 3 laboratory abnormalities under treatment and shifts in toxicity grading from Cycle 1 Day 1 to highest grade post-Cycle 1 Day 1 will be displayed. Results for variables that are not coded will be presented in the listings as below, within, and above the normal limits of the local laboratory.
 
Vital sign measurements will be summarized at each scheduled time point using descriptive statistics. ECOG performance status results will be summarized by scheduled time point. Additional statistical details will be provided in a prospective statistical plan.
 
Tesevatinib concentrations in the plasma and CSF will be summarized at each scheduled collection time point using descriptive statistics, and displayed graphically.

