- c: Safety labs = hematology and clinical chemistry and urinalysis. Note that Cycle 1 Day 1 labs need not be repeated if screening visit occurred within 4 days prior to Day 1 visit. Safety labs will also be done at C2D15, C3D15, C4D15, C5D15, and C6D15; they are to be done locally and will include serum chemistry only. There will be a 3 day window for the D15 chemistry labs. Cystatin C does not need to be included in the chemistry labs done on C2D15, C3D15, C4D15, C5D15, and C6D15.
 - d: Pregnancy tests will be done using urine samples in women of childbearing potential. Subject must have a negative urine pregnancy test documented within the 24-hour period prior to the first dose of study drug. Confirm with serum testing if urine sample is positive..
 - e: Supine 12-Lead ECGs will be performed at screening; Days 1, 7 and 14 of Cycle 1; on Day 1 of Cycles 2 and Day 1 of each Cycle including at End of Study Drug Treatment visit Assessment to be performed at predose, and once within 4 – 8 hours postdose for Days 1, 7 and 14 of Cycle 1. At each timepoint, repeat ECG three times consecutively within 30 minutes (must have an interval of at least 1–2 minutes between ECGs).
 - f: Tumor assessment is to be performed at screening, at C2D1, on C3D1, and after every 2 cycles (beginning on Day 1 of Cycle 3 [\pm 7 days]). Tumor assessment should include brain MRI. Peripheral (non-CNS) tumor may be assessed with either CT or MRI, but method of assessment should be the same throughout the study. Tumor assessment on C2D1 will be limited to brain MRI.
 - g: Bone scans are to be performed at screening and then as clinically indicated.
 - h: Tesevatinib will be administered at the dose of 300 mg once daily.
 - i: EORTC QLQ-C30 and EORTC QLQ-BN20 questionnaires administered at screening, on Day 1 of Cycle 3, and on Day 1 of odd-numbered cycles thereafter and EOS
 - j: AEs are to be collected from the time of informed consent through 30 days after last dose of study drug.
 - k: The End-of-Study Drug Treatment visit is to occur within 3 days after the subject's last dose of study drug. This may occur at the visit at which disease progression is diagnosed. Tumor assessment does not need to be performed if it was performed in the previous 8 weeks.

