9.1.6 Hematology, Serum Chemistries, and Urinalysis

Samples for laboratory assessments (hematology, serum chemistries, and urinalysis) are to be collected. A central laboratory will perform hematology, serum chemistry, and urinalysis tests and results will be provided to the investigator. Blood and urine samples for hematology, serum chemistry, and urinalysis will be prepared using standard procedures. Laboratory panels are defined as listed in Table 9-1. In addition to central laboratory testing, a local laboratory will perform serum chemistry tests on Day 15 of each cycle from Cycle 2 through Cycle 6 for additional safety data. The local laboratory will perform all the serum chemistry tests included in Table 9-1 with the exception of Cystatin C.

Table 9-1: Clinical Laboratory Panels

Hematology	Serum Chemistry	Urinalysis

 Red blood cell count WBC with differential (including neutrophils, basophils, eosinophils, lymphocytes, monocytes) hemoglobin hematocrit platelet count mean corpuscular volume (MCV) mean corpuscular hemoglobin (MCH) mean corpuscular hemoglobin concentration (MCHC) 	
 albumin amylase alkaline phosphatase ALT AST bicarbonate BUN calcium chloride creatinine creatine phosphokinase phosphorous potassium random glucose sodium total & direct bilirubin total protein magnesium cystatin C 	
 appearance color pH specific gravity ketones leukocytes protein glucose bilirubin urobilinogen occult blood (microscopic examination of sediment will be performed only if the results of the urinalysis dipstick evaluation are positive)
Other		

 Fasting triglycerides^a 		

ALT = alanine aminotransferase; AST = aspartate aminotransferase; BUN = blood urea nitrogen; MCH = mean corpuscular hemoglobin; MCHC = mean cell hemoglobin concentration; MCV = mean cell volume

^a To be drawn in the event that amylase increases to $> 1.5 \times \text{ULN}$.

Abnormalities in clinical laboratory tests that lead to a change in subject management (e.g. dose delay, requirement for additional medication or monitoring) are considered clinically significant for the purposes of this study, and will be recorded on the AE electronic case report form (eCRF) page. If laboratory values constitute part of an event that meets criteria defining it as serious, the event (and associated lab values) must be reported as an SAE (see Section 15.3.11).

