15.3.9 Laboratory and ECG Abnormalities

For the purposes of grading creatinine, the ULN – not the subject's Cycle 1 Day 1 value - will be used to determine grade.

For the purpose of grading sodium, values of 126–130 mmol/L will be considered to be Grade 2 and values of 120–125 mmol/L will be considered Grade 3.

For the purposes of this study, ECG abnormalities will be handled in the same manner as laboratory abnormalities.

Non-Clinically Significant (NCS) Laboratory Abnormalities

All laboratory results must be filed in the subject's medical record and be monitored. The investigator must review laboratory results in a timely manner demonstrated by signature/date and assignment of clinical significance assessment. Non-clinically-significant laboratory abnormalities, i.e., minor deviations from the normal range, are expected and it is likely that no medical intervention will be required. Such results will not be considered to be AEs.

Clinically Significant (CS) Laboratory Abnormalities

Any laboratory abnormality that is considered to be clinically significant by the investigator will be recorded on the AE eCRF. A clinically significant abnormal test result will be considered an AE if:

- It is not associated with an already reported AE, diagnosis or pre-existing condition;
- There is a change in concomitant medication or intervention as needed, in direct response to the laboratory result;
- The investigator exercises his/her discretion to make significance determinations for any subject laboratory result or result that requires intervention.

All such lab abnormalities will be repeated and assessed by the investigator, or licensed (MD), as soon as possible for "seriousness" and if they meet the regulatory definition of "serious", they will be reported as SAEs following regulatory and protocol requirements. Repeat laboratory tests may be run in order to monitor the result.

Serious Laboratory Abnormalities

Any lab abnormality meeting the regulatory definition of "serious" must be recorded on both the AE eCRF/record and the SAE Form. If a subject experiences a serious toxicity or dies, the FDA will be notified within 24 hours, as required.

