## 2 Statistical Methods

No formal hypothesis testing will be conducted. Descriptive statistics including 95% confidence intervals for response rate, time-to-event and continuous measurements will be summarized by cohorts.

Tesevatinib concentrations in the plasma and CSF will be summarized at each scheduled collection time point using descriptive statistics, and displayed graphically.

AEs, SAEs, Grade 3&4 AEs, related AEs, related SAEs, related Grade 3&4 AEs, death, and AEs leading to withdrawal, dose modification, or treatment discontinuation will be summarized by cohort and overall according to high level terms (HLT) and preferred terms (PT). Adverse events will also be summarized in listings. Duration of AEs will be determined and included in listings, along with action taken and outcome.

Vital sign measurements will be summarized at each scheduled time point using descriptive statistics. The ECOG performance status results will be summarized by scheduled time point.

Laboratory results will be classified according to NCI-CTCAE Version 4.03 and summarized by cohort. The worst on-study grade after the first dose of study drug will be summarized. The incidence of ≥ Grade 3 laboratory abnormalities under treatment and shifts in toxicity grading from Cycle 1 Day 1 to highest grade post-Cycle 1 Day 1 will be displayed. Results for variables that are not coded will be presented in the listings as below, within, and above the normal limits of the local laboratory.

The table of list of tables, listings, and figures is displayed in Table 1.

 Table 1 Content of efficacy tables

| T/F/L | Number | Title   | Order                        | Population                    | Summary Statistics            |
|-------|--------|---|------------------------------|-------------------------------|-------------------------------|
| T     | 1.1.1  | Response rate by cohort   | Primary efficacy             | All treated subjects          | ORR, CR, PR, exact CI         |
| Т     | 1.1.2  | Response rate by visit and cohort                                   | Primary efficacy             | All treated subjects          | ORR, CR, PR, exact CI         |
| L     | 1.1.1  | Tumor size / symptoms and signs by visit and cohort                 | Primary efficacy             | All treated subjects          |                               |

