## Statistical Analysis Plan

| L | AE  | 6.1.2 | AE Leading to Treatment Discontinuation  | All treated patients |
|---|-----|-------|--|----------------------|
| L | AE  | 6.1.4 | Death  | All treated patients |
| Т | Lab | 7.1.1 | Lab values and their change from baseline by cohort Shifts in toxicity grading from baseline to highest grade post-baseline of | All treated patients |
| T | Lab | 7.1.3 | laboratory abnormalities by cohort   | All treated patients |
| L | Lab | 7.1.1 | Lab values with CTCAE grade >= 3   | All treated patients |
| T | VS  | 8.1.1 | Vital signs and their change from baseline by cohort   | All treated patients |
| L | VS  | 8.1.1 | Vital signs  | All treated patients |
| L | VS  | 8.2.1 | Physical examinations  | All treated patients |
| T | ECG | 9.1.1 | ECG parameters and their change from baseline by cohort  | All treated patients |
| T | ECG | 9.2.1 | QTcF abnormalities by cohort   | All treated patients |
| L | ECG | 9.1.1 | ECG values   | All treated patients |

Abbreviations: AE = adverse event; CNS = central nervous system; CSF = cerebrospinal fluid; CTCAE = Common Terminology Criteria for Adverse Events; DNA = deoxyribonucleic acid; ECG = electrocardiogram; EGFR = epidermal growth factor receptor; HLT = high level terms; MRI = magnetic resonance imaging; NSCLC = non-small cell lung cancer; OS = overall survival; PFS = progression-free survival; TEAEs = treatment-emergent adverse events; VS = vital signs

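### Uncoded laboratory results are judged against the wrong laboratory's limits, and no planned table pairs creatinine with cystatin C within a subject

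*Protocol*

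**What the plan says.** **Why cystatin C is measured.** Protocol 5.2.1 describes nine subjects on 50 mg in the polycystic kidney disease study. Their median "creatinine values were increased by 7.5% at Day 3, by 22% at Day 7, and increased by 13% at Day 28", while cystatin C did not change. It explains the rise by inhibition of MATE transporters and notes that earlier studies, lacking cystatin C, could not recognise rises that were not renal. It then says of this trial: "Both serum creatinine and cystatin C will be evaluated in this study in order to provide more information about any changes in creatinine". Section 11.1.3.5 also calls for cystatin C in the clinical work-up once creatinine exceeds 2 x ULN.

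**How creatinine is analysed.** Protocol 15.3.9 says that the ULN, not the subject's "Cycle 1 Day 1 value - will be used to determine grade". SAP Section 2 states: "Laboratory results will be classified according to NCI-CTCAE Version 4.03 and summarized by cohort". Creatinine grades therefore enter the worst-grade summary and the shift table T 7.1.3.

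**How uncoded results are handled.** Protocol 16.3.7 leaves results without a coded term ungraded. The synopsis, Section 16.3.7 and SAP Section 2 all place uncoded variables in listings, classified as "below, within, and above the normal limits of the local laboratory".

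**Who analyses what.** Section 9.1.6 states: "A central laboratory will perform hematology, serum chemistry, and urinalysis tests". Local laboratories add only serum chemistry on Day 15 of Cycles 2 to 6. Footnote c of Tables 4-1 and 4-2 says: "Cystatin C does not need to be included in the chemistry labs done on C2D15", and continues with the other four Day 15 draws.

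**Planned SAP outputs.** T 7.1.1 gives laboratory values and change from baseline by cohort. The only laboratory listing, L 7.1.1, is titled "Lab values with CTCAE grade >= 3". The SAP does not mention cystatin C.

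**The concern.** Two separate problems meet here.

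The reference-limit rule names a laboratory that did not analyse most of the samples. A below, within or above flag is meaningful only against the range of the laboratory and assay that produced the value. As written, the rule applies one laboratory's range to another laboratory's results.

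The protocol also gives a reason for measuring cystatin C that depends on reading it beside creatinine, and no SAP output does so. If one subject has a transporter effect and another has kidney injury, both can fall in the same cell of T 7.1.3. Both are plausible in this trial: Section 5.2.1 documents MATE inhibition and expects diarrhea, and Section 11.1.3.5 names dehydration from diarrhea as a cause to look for when creatinine is high. At stake is whether the safety tables can answer, for an individual subject, the question that cystatin C was added to inform.

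**Working it through.** The documents give no figure to reproduce on this point. The check sets the rules side by side, counts scheduled draws and adds one illustration.

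**1. Which laboratory analyses each panel (through Cycle 6)**

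- Central: Screening, C1D1, C1D7, C1D14 (4), Day 1 of Cycles 2 to 6 (5), end of treatment and 30-day follow-up (2). 4 + 5 + 2 = 11.
- Local: Day 15 of Cycles 2 to 6, chemistry only = 5.
- Hematology and urinalysis: 11 of 11 panels central.
- Chemistry: 11 + 5 = 16 panels, of which 11 are central. The local share is 5/16 = 31%.
- Cystatin C: in the central chemistry panel (Table 9-1), and in none of the 5 local panels.

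So the local range fits only uncoded results from the 5 Day 15 chemistry panels. It does not fit uncoded results from the other panels.

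**2. Creatinine values without a paired cystatin C**

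| Post-dose draws through Cycle 6 | Creatinine | Cystatin C |
|---|---|---|
| C1D7, C1D14, Day 1 of Cycles 2–6 (central) | 7 | 7 |
| End of treatment, 30-day (central) | 2 | 2 |
| Day 15 of Cycles 2–6 (local) | 5 | 0 |
| Total | 14 | 9 |

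Unpaired: 5/14 = 36%. Without the end-of-treatment and 30-day visits: 5/12 = 42%.

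**3. What each planned output can show**

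- T 7.1.1: change in each marker by cohort, as separate summaries. No within-subject link.
- T 7.1.3: creatinine grade shift. Cystatin C does not appear if it is ungraded.
- L 7.1.1: Grade 3 or higher only, so an ungraded analyte cannot appear, although SAP Section 2 says uncoded results will be listed.

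None shows, for a given subject, the creatinine grade beside the cystatin C change.

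**4. Illustration of how easily a grade can move**

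Assume that Grade 1 starts just above the ULN (the documents give no threshold) and that the 50 mg medians carry over to 300 mg. The baseline at which a rise r reaches the ULN is 1/(1 + r):

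- r = 22% (Day 7): 1/1.22 = 0.82 x ULN
- r = 13% (Day 28): 1/1.13 = 0.88 x ULN
- r = 7.5% (Day 3): 1/1.075 = 0.93 x ULN

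By contrast, a 22% rise reaches 2 x ULN, the level named in Section 11.1.3.5, only from a baseline of 2/1.22 = 1.64 x ULN. A rise of the expected size can thus change a grade without reaching the level at which that section brings in cystatin C.

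**The case against.** The case against has real force, and it limits the point in several ways.

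- **A reader might infer that the safety outputs cannot separate the two mechanisms at all.** The documents do not support that. T 7.1.1 excludes no analyte, so changes in creatinine and cystatin C by cohort should both be reported. That is the kind of evidence on which Protocol 5.2.1 itself relies. Protocol Section 16 also promises listings of all captured clinical data. What remains is the subject level: a cohort summary of at most 20 subjects can stay flat while a few subjects have both markers rise, and the SAP's own output list contains no listing that would show it.
- **A reader might infer that no local limits exist for cystatin C.** The documents show only that the study's local panels do not run it. They are silent on whether local laboratories hold a range.
- **A reader might infer that a transporter effect will be reported as renal toxicity.** T 7.1.3 shows grade shifts in laboratory abnormalities and assigns no cause. Under Section 15.3.9, abnormalities that are not clinically significant are not adverse events.
- **The unpaired share overstates the loss.** Section 5.2.1 says that the rise comes early and does not continue after about Day 7. C1D7, C1D14 and C2D1 are all central and paired; the first unpaired draw, C2D15, is Day 28 + 15 = 43. This stands: those values need a label, not extra tests.
- **Renal differentiation is not a study objective**, and the study is descriptive with up to 60 subjects. This also stands. It limits the weight of the point but does not remove the mismatch in limits or the unused pairing.

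**Conclusion.** The point holds in two parts.

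The reference-limit rule contradicts the laboratory arrangements in Section 9.1.6. It is wrong for every uncoded result from a central panel. That it is wrong for cystatin C in particular rests on the assumption that cystatin C has no CTCAE term; no document grades it, but none says so. If it were graded, the rule would still be wrong for other uncoded central results.

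The planned SAP tables cannot show at subject level whether a graded creatinine rise came with a cystatin C rise, although the nine paired post-dose draws through Cycle 6 would allow it. This part does not depend on the CTCAE assumption.

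The 0.82 and 0.88 x ULN figures are illustrations only. They use medians from nine subjects with a different disease at 50 mg, and the documents give no basis for estimating how many subjects would be affected here. No efficacy result changes and no data are lost. This is a correction worth making before the safety outputs are programmed.

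**What to change.** 1. In the Protocol synopsis, Protocol 16.3.7 and SAP Section 2, replace the reference to local limits with *the normal limits of the laboratory that analysed the sample*: central for scheduled panels and all scheduled cystatin C, local for Day 15 chemistry.
2. Add one output to SAP Table 2, for all treated subjects, pairing the percent change from baseline in creatinine and in cystatin C from the same central sample. Show creatinine grade shift against both the cystatin C percent change and its status relative to the central ULN. Mark Day 15 creatinine values as unpaired. Baseline is Cycle 1 Day 1, or screening where the Day 1 sample was not repeated, as footnote c allows.

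Two features matter. Including all treated subjects keeps those whose creatinine rises without a grade change, such as a 22% rise from below 0.82 x ULN under the illustration. Showing percent change as well as ULN status keeps a cystatin C rise within the normal range visible.

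The cost is one phrase in three places and one extra table. No new test or visit is needed.
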